7.3. Withdrawal criteria

Based on the provisions of the Declaration of Helsinki, the subjects have the right to withdraw from the study at any time and for any reason, being able to express it personally or through their representative. The investigator reserves the right to withdraw any subject from the study in the following cases:

- Subject abandonment: violation of inclusion or exclusion criteria or non-cooperation. In case of withdrawal, the reason is reflected in the Data Notebook.
- By efficacy criteria: if, in the investigator's opinion, the product is not causing any benefit to the subject under study.
- Due to safety criteria: in the event of a serious or unexpected adverse event and that, for this reason, or due to the medication that may be instituted to reverse such event, it is considered that its continuation in the study is not pertinent.

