2.7. Expected duration of the study

The overall duration of the study is expected to be 12 months from the start of recruitment of the populations until the last follow-up control and analysis of the data generated.

The intervention (application of the cosmetic cream) will take place from the beginning to the end of the chemotherapy treatment, with 1 daily application of the product (PB-011 or PB-012) on the hands. If sensory discomfort or, in the worst case, peripheral neuropathy develops during the period of chemotherapy or immunocytostatic treatment, the application shall be increased to twice daily on the affected areas (usually hands and feet). In case of lack of efficacy of the product, the investigator in charge may withdraw the subject from the study after three months of application of the product.

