7.2. Study development

When a subject meets all the inclusion criteria and none of the exclusion criteria and has signed the informed consent document, he/she is electable to enter the study. The researchers will collect the data of each volunteer and notify Prospera Biotech of their inclusion. Patients will

receive the cream when they start the chemotherapy treatment. Creams will be either sent directly to the participants' home or sent in advance to the centers and stored there at room temperature (15-25°C) until distributed to participants. The principal investigator will create the Data Notebook for each subject, anonymizing the personal and clinical data in all cases. The type of product to be assigned will be determined by the randomization procedure.

Subjects taking part in the study should apply a sufficient amount of cream to their hands once a day for the duration of their chemotherapy treatment. Those subjects who develop skin sensitivity or peripheral neuropathy should undergo the following procedures:

1. Increase the frequency of use of the cream to twice a day in all affected areas.
2. Once the chemotherapy treatment is finished: evaluation of the degree of skin satisfaction by means of a questionnaire that assesses the Dermatology Life Quality Index [DLQI] (Annex II) and the degree of satisfaction with the cream (Annex IV). Evaluation of the discomfort generated by peripheral neuropathy through a follow-up questionnaire (Annex III). Measurement of skin sensitivity using Von Frey hairs for patients who voluntarily wish to do so. These procedures will be carried out by the study collaborators of each center. In case of need, Prospera Biotech team could also contribute to make the follow-up (questionnaires) telematically.

The study procedures are included in section 8.2.

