11.2. Protocol deviations

When a situation that causes a deviation from the protocol occurs, the deviation will be only for that subject. Investigators present in such circumstances will fully document the deviation and reason on the Data Notebook. In the event that the deviation has to do with the inclusion/exclusion criteria, the investigators will contact the clinical monitor by telephone in order to inform them of such deviation.

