12. STATISTICAL ANALYSES

The analysis of the results of this study will be approached from two perspectives. On the one hand, the modified intention-to-treat (MITT) population will be analyzed, which corresponds to all those subjects who have used the product at least once and for whom satisfaction data is available. On the other hand, a per-protocol analysis will be carried out in which all randomized subjects who have followed the study instructions until the end of the study will be included.

The clinical evaluation data may be analyzed as quantitative or qualitative variables. In the first case, the results will be expressed as mean \pm standard deviation, minimum and maximum. In the case of qualitative variables, the results will be expressed as frequency and percentage. For all the parameters to be measured (both clinical variables and responses to questionnaires) there will be a baseline measurement taken before the start of the protocol that will serve as a control measurement. The change in the main variable (degree of satisfaction) will be analyzed

using the paired Student's T test. The change in the secondary variables will be studied according to their nature (qualitative or quantitative variables) and applying the corresponding test in each case: Chi square, Student's T, ANOVA, Kruskal-Wallis or Mann-Whitney U. The impact of each variable on the main variable will be assessed, especially the impact of treatment, diagnosis, age and gender.

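### Section 7.3 allows withdrawal from the study for eligibility breach, undefined non-cooperation or lack of benefit, with no outcome collection afterwards, so mITT can lose patients for reasons tied to the outcome

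*Combined protocol and SAP*

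**What the plan says.** **Withdrawal.** Section 7.3 states: "The investigator reserves the right to withdraw any subject from the study in the following cases". The first case is "Subject abandonment: violation of inclusion or exclusion criteria or non-cooperation", followed by "In case of withdrawal, the reason is reflected in the Data Notebook". The second is "By efficacy criteria: if, in the investigator's opinion, the product is not causing any benefit to the subject under study". The third concerns safety and is not part of this point. Non-cooperation is not defined. Section 2.7 also covers lack of efficacy, saying that "the investigator in charge may withdraw the subject from the study after three months of application of the product"; 7.3 carries no such time limit.

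**Deviations.** Section 11.2 has deviations and their reasons documented in the Data Notebook and confined to the subject concerned. It adds: "In the event that the deviation has to do with the inclusion/exclusion criteria, the investigators will contact the clinical monitor by telephone". It does not mention withdrawal and does not refer to 7.3.

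**Timing of the outcome.** For patients who develop skin sensitivity or neuropathy, section 7.2 sets out "Once the chemotherapy treatment is finished: evaluation of the degree of skin satisfaction by means of a questionnaire", and section 8.2 agrees. Section 3 instead has satisfaction assessed every fortnight when there is discomfort. Section 12 promises a baseline measurement of all parameters, questionnaires included.

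**Analysis sets.** Section 12 defines mITT as "all those subjects who have used the product at least once and for whom satisfaction data is available". Per-protocol keeps randomised subjects who followed the instructions to the end.

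The available text has no rule for collecting outcomes after withdrawal, no missing-data method, and no dropout allowance in section 6.3.

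**The concern.** Stopping a cream and leaving the study are different events, but section 7.3 speaks only of withdrawal from the study. The trial sets out to compare acceptance of two creams, and section 3 describes acceptance as central to adherence. A patient who dislikes a cream may apply it less, be judged non-cooperative and be withdrawn. A patient who gets no relief may be withdrawn for lack of benefit, which is tied to the outcome even more directly.

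If those patients then supply no questionnaire, they can leave mITT as well as per-protocol. mITT would then be a weaker check on the per-protocol result, and an arm with poorer acceptance could look better than it was. This does not require unblinding: if acceptance differs between the creams, so can removal.

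There are two lesser difficulties. Sites have no rule for when an eligibility breach stays a deviation under 11.2 and when it leads to withdrawal under 7.3, so like cases can be handled differently. The abandonment heading also puts investigator decisions under a name that suggests the patient left.

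**Working it through.** **1. Follow one patient through the sections.** A randomised patient uses the cream and is withdrawn under 7.3 before chemotherapy ends.

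- Under 7.2 and 8.2 the questionnaires fall after chemotherapy, so none is due before withdrawal, and no text provides for one afterwards.
- Under section 3, a patient with discomfort might have fortnightly values. Sections 7.2 and 8.2 contain no such visits, and no rule says an earlier value may replace the final one.
- Under section 12 a baseline exists. But the main variable is analysed as a change, so a baseline alone contributes nothing, and satisfaction with a cream cannot be measured before it is used.

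Such a patient would therefore usually have no post-baseline satisfaction data and could drop out of mITT. A non-adherent patient who is not withdrawn and completes the questionnaire stays in.

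**2. The plan's own figure.** Inputs from section 6.3: difference 2, SD 3, significance level 0.05 (two-sided assumed), power 95%.

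n per arm = 2 × 3² × (1.960 + 1.645)² / 2² = 58.5, so 59. The t-test version gives 59.45, so 60. The stated 60 reproduces, with no dropout allowance.

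**3. Lost numbers alone.** The documents give no withdrawal rate, so the losses below are assumed.

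| Loss | Left per arm | Power, normal (t-based) |
|---|---|---|
| 0% | 60 | 95.5% (95.2%) |
| 5% | 57 | 94.5% (94.2%) |
| 10% | 54 | 93.4% (93.0%) |
| 20% | 48 | 90.4% (89.8%) |
| 30% | 42 | 86.3% (85.5%) |

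The loss of power from moderate withdrawal is small. Selection matters more.

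**4. Worst-case illustration of selection.** Assume normal scores with SD 3 (section 6.3), and that exactly the lowest-scoring fraction p is removed from one arm and nobody from the other.

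Shift in that arm's mean = 3 × φ(z_p) / (1 − p)

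- p = 5%: 3 × 0.1031 / 0.95 = 0.326 points, 16% of the 2-point difference
- p = 10%: 3 × 0.1755 / 0.90 = 0.585 points, 29%
- p = 20%: 3 × 0.2800 / 0.80 = 1.050 points, 52%

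Removal at random, or equal removal in arms with the same score distribution, gives no shift in the difference.

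**5. Limits of that illustration.** The scale is bounded at 0. If the arm mean were 5 (assumed), the removed 5% would average 5 − 3 × 0.1031 / 0.05 = −1.19 and the removed 10% would average 5 − 3 × 0.1755 / 0.10 = −0.27, both impossible. With a floor of 0 the shift cannot exceed p × 5 / (1 − p), which is 0.26 at 5% and 0.56 at 10%. At 20% the removed average is 5 − 3 × 0.2800 / 0.20 = 0.80, so this floor does not bind. The scale is also the 0-10 planning scale of 6.3, whereas section 8.1 names the DLQI as the main variable.

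**The case against.** **Sections 7.3 and 11.2 do not contradict each other.** This stands. A reader might infer from 11.2 that the patient must stay, but it is silent on retention. A breach can be documented there and also lead to withdrawal under 7.3. The sections are unlinked, which leaves sites without a rule.

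**Satisfaction data do not come only at the end.** This stands in part. Section 3 (fortnightly) and section 12 (baseline) conflict with 7.2 and 8.2, so one cannot say that an early-withdrawn patient can never have satisfaction data. Step 1 shows why that patient would still usually lack a usable post-baseline value.

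**mITT has no compliance condition, and withdrawal is discretionary.** This stands. A reader might infer that mITT shrinks to the compliant patients or becomes almost identical to per-protocol. That would need frequent use of the power, and the documents give no rate.

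**The reason for withdrawal is recorded.** This stands. Investigator removals are not hidden and could be tabulated. What remains is a heading that mixes two kinds of event and no plan to report them by arm.

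**Larger routes of selection exist.** Lack-of-benefit withdrawal is closer to the outcome and belongs in the same fix. Giving end-of-treatment questionnaires only to patients with discomfort (7.2, 8.2) may remove more patients from mITT than non-cooperation does. Retaining an asymptomatic patient adds no end-of-treatment data under that rule.

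**Conclusion.** The point holds as a gap in the plan. Section 7.3 permits post-randomisation removal on grounds that can depend on acceptance, section 12 makes mITT depend on available data, and no text keeps outcome collection going after withdrawal. mITT can therefore move towards the per-protocol set.

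The size of any bias cannot be calculated from the documents. The 0.33 to 1.05 point range is a one-arm worst case under normality on the planning scale. It should not be read as an expected effect in this trial or as a shift in the DLQI. The cost in power is modest: about 93% with an assumed 10% loss, instead of about 95%.

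The conclusion rests on reading 7.2 and 8.2 as the operative schedule and on there being no follow-up rule elsewhere. The Data Notebook (Annex I) is a separate attachment and could not be checked. On that basis the change is worth making because it is cheap and protects the comparison.

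**What to change.** - Reconcile 7.3 with 11.2, define non-cooperation, and separate stopping the product from leaving the study. When the product is stopped is for the sponsor and investigators to decide. Sections 2.7 and 7.3 must be reconciled on the timing of lack-of-benefit withdrawal.
- State that patients with an eligibility breach, non-cooperation or perceived lack of benefit stay in follow-up unless they withdraw consent, and complete the planned end-of-chemotherapy questionnaires on the same basis as other patients.
- Analyse them in mITT in the assigned arm. Leave them out of per-protocol only where they did not follow the study instructions.
- Reconcile sections 3, 7.2, 8.2 and 12 on when satisfaction is measured, and state a missing-data method.
- Record investigator-initiated and patient-initiated withdrawals as separate categories and report both by arm.

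**Cost.** Amendment wording, possibly a field in the Data Notebook, and a few more questionnaires of a kind already planned. mITT will include some non-adherent patients, which may dilute a difference; section 12's one-use criterion already admits such patients.

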8. STUDY DEVELOPMENT AND EVALUATION OF THE RESPONSE

8.1. Study variables

Main Variable: degree of skin satisfaction/comfort with the skin in the palmar and plantar regions, evaluated by means of the DLQI questionnaire.

Secondary Variables:

- Skin sensitivity quantifiable by the Von Frey filament test for patients who voluntarily so wish.
- Follow-up of discomfort skin sensations experienced by patients, evaluated by means of a brief questionnaire.

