1. SUMMARY

A pilot controlled clinical study is proposed to evaluate and compare the degree of satisfaction and skin comfort with cosmetic creams PB-011 and PB-012 in oncology patients who have developed palmar and plantar peripheral poly-neuropathy due to treatment with chemotherapy or chemotherapeutic agents fused to monoclonal antibodies (immunocytostatic). Both products are cosmetic creams derived from the line Nocisens (for the care of sensitive skin with atopic tendency). The hypothesis to be tested is that care with PB-011 or PB-012 for sensitive skin associated with palmar and plantar peripheral poly-neuropathy in oncology patients will increase their degree of satisfaction and skin comfort. A parallel, randomised, double-blind, masked, double-blind study is proposed in patients who are about to start chemotherapeutic treatment. The study involves two populations: (i) the population where PB-011 cream will be tested; and, (ii) the population that will test PB-012 cream. The duration of the project will be 12 months, and participants will have to apply the cream on their hands once a day during the period of chemotherapy treatment. A sample size of 60 volunteers per population has been estimated to ensure statistical significance. As a relevant qualitative variable for patients who have developed neuropathy, the degree of satisfaction and skin comfort will be assessed by means of a questionnaire.

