2.3. Description of the products under study

Product: Cosmetic creams with Ref. PB-011 and PB-012

Trade name: Nocisens. The formulation with the best acceptance in the study population will be marketed under the name Oncapsisens.

Commercial name: Prospera Biotech S.L

Code and INCI:

- PB-011: Capric Triglyceride, Glyceryl Behenate, Glyceryl Stearate, Hydrogenated Castor Oil, Diethylene Glycol Monoethyl Ether, Tocopherol, Hydroxymethoxyiodobenzyl Glycolamide Perlargonate.
- PB-012: Capric Triglyceride, Glyceryl Behenate, Glyceryl Stearate, Hydrogenated Castor Oil, Diethylene Glycol Monoethyl Ether, Tocopherol.

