The Institute for Research, Development and Innovation in Health Biotechnology of the Miguel [name] University of Elche (IDIBE-UMH) has been studying the mechanisms that govern skin imbalances for many years. This knowledge has been transferred to Prospera Biotech, and has been used to develop a line of creams for sensitive skin (trade name Nocisens). The mixture of fatty acids, tocopherol and innovative cosmetic ingredients means that Nocisens has a dual action on the stratum corneum. On the one hand, it strengthens the skin's barrier function by preventing water loss, which helps to increase hydration and re-establish the skin's protective function and, on the other hand, it prevents the accumulation of reactive oxygen species in the cells, protecting the skin from their harmful effects. These two actions help Nocisens cosmetic cream to create a feeling of well-being and comfort for the skin.

However, in cosmetics, the degree of acceptance of a product is a key element for adherence to treatment. We have therefore developed two formulations derived from Nocisens, PB-011 and PB-012, with slightly different texture, composition and properties in order to adapt them to the needs of the sensitive skin characteristic of palmo-plantar neuropathy mediated by chemotherapeutics.

Given that PN induced by treatments with chemotherapy or chemotherapeutic agents fused to monoclonal antibodies (immunocytostatic) is characterised by skin imbalances that affect the quality of life of the people who suffer from it, a parallel, randomised, double-blind, masked study is proposed in patients who are about to begin oncological treatment to compare the

degree of acceptance of PB-011 and PB-012 cosmetic creams in this population. The study involves two populations: (i) the population where PB-011 cream will be tested; and, (ii) the population that will test PB-012 cream. The duration of the project will be 12 months, and participants will have to apply the cream once a day on their hands during the period of chemotherapy treatment. A sample size of 60 volunteers per population has been estimated to ensure statistical significance. As a relevant variable for the patients, the degree of skin satisfaction will be assessed every fortnight by means of a questionnaire only in the case of discomfort in the hands and/or feet.

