4. JUSTIFICATION AND STUDY OBJECTIVES

The toxicity generated during chemotherapy treatments can usually produce skin discomfort or peripheral polyneuropathy. CIPN manifests itself above all in the extremities, mainly in the palmar and plantar regions, giving rise to uncomfortable sensations such as itching, numbness, tingling, pain or dryness, i.e. skin sensitivity. Currently, there is no specific treatment to combat this skin sensitivity and oncology specialists recommend keeping the skin hydrated through the use of cosmetic creams.

Taking into account that these sensations imply a deterioration in the quality of life of patients, our hypothesis is that cosmetic creams for sensitive skin with references PB011 and PB012 could improve comfort and the degree of satisfaction of cancer patients with CIPN. The reason for this hypothesis is that cosmetic creams contain ingredients that reinforce the barrier function of the epidermis and improve the hydration and appearance of the skin. The study has been designed to define which of the two creams produces greater satisfaction in patients.

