ANNEX IV: SATISFACTION QUESTIONNAIRE

Title: Study for the evaluation of the degree of skin satisfaction of cosmetic creams PB-011 and PB-012 for sensitive skin in oncological patients affected by a palmoplantar polyneuropathy secondary to taxanes.

Principal Investigator: [name]

Reference: 20PB-02

1. Has applying the cream to your hands and/or feet caused you any discomfort?

Nothin									Many
1	2	3	4	5	6	7	8	9	10

2. Has the application of the cream to your hands and/or feet generated any kind of skin reaction?

Nothin									Many
1	2	3	4	5	6	7	8	9	10

3. How would you define your degree of satisfaction with the cream?

Nada									Mucho
1	2	3	4	5	6	7	8	9	10

If, sensorial discomfort or CIPN have appeared during the chemotherapy treatment please answer also:

1. When you apply the cream to your hands and/or feet, do you feel any relief from any of the sensations that bother you?

YES	NO
-----	----

2. Has the application of the cream generated comfort in your skin sensitivity on the hands

and/or feet?

Nothing										A lot
1	2	3	4	5	6	7	8	9	10	

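### Satisfaction with the cream (Annex IV) is collected and is the question the trial asks, but section 8.1 gives it no place among the study variables, and the sample size fits it rather than the DLQI

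*Combined protocol and SAP*

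**What the plan says.** **Purpose and decision.** Section 4: "The study has been designed to define which of the two creams produces greater satisfaction in patients". Section 3 proposes to compare the "degree of acceptance of PB-011 and PB-012 cosmetic creams in this population". Section 2.3 names a decision: "The formulation with the best acceptance in the study population will be marketed under the name Oncapsisens". The Summary (section 1) is broader, and sets out to "evaluate and compare the degree of satisfaction and skin comfort with cosmetic creams PB-011 and PB-012".

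**Variables.** Section 8.1 gives one main variable: "Main Variable: degree of skin satisfaction/comfort with the skin in the palmar and plantar regions, evaluated by means of the DLQI questionnaire". It gives two secondary variables: "Skin sensitivity quantifiable by the Von Frey filament test for patients who voluntarily so wish" and "Follow-up of discomfort skin sensations experienced by patients, evaluated by means of a brief questionnaire". Section 8.2 ties the second of these to Annex III, a derivative of the Leonard Scale.

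**Collection.** Sections 7.2 and 8.2 ask patients who develop sensory or skin discomfort to complete the DLQI (Annex II), the discomfort questionnaire (Annex III) and the cream-satisfaction questionnaire (Annex IV) at the end of chemotherapy. Item 3 of Annex IV asks "How would you define your degree of satisfaction with the cream", scored 1 to 10.

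**Sample size and analysis.** Section 6.3 assumes a 2-point difference between creams on a 0-10 satisfaction scale (or 2 points on the Von Frey scale), SD 3, significance at 0.05 and 95% probability of detection, giving 60 per arm. Section 12 calls the main variable degree of satisfaction without naming an instrument. It analyses its change with a paired t test.

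**The concern.** The outcome closest to the trial's question has no rank. Annex IV is the only instrument printed in the protocol that asks patients to judge the cream, yet it is neither the main variable nor a secondary one. Sections 7.2 and 8.2 list skin satisfaction by DLQI and satisfaction with the cream by Annex IV as two separate assessments, so the protocol itself does not treat one as a stand-in for the other.

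Two things are at stake. First, section 2.3 promises a product choice on acceptance, but no listed variable measures acceptance and no rule links the choice to a result. Second, sections 6.3, 8.1 and 12 use the word satisfaction for what could be two different instruments. That leaves open, until after the data are seen, which score the main result refers to.

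**Working it through.** **1. Reproduce the sample size.** Inputs from section 6.3: difference 2, SD 3, alpha 0.05, power 95%. Sidedness is not stated; two-sided is taken because it reproduces the figure.

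- Normal approximation: n = 2 × (1.960 + 1.645)² × 3² / 2² = 2 × 13.0 × 2.25 = 58.5, so 59 per arm.
- Two-sample t test: 59.5, so 60 per arm.
- Power at 60 per arm: 95.5% (normal) or 95.2% (t test).
- One-sided alpha would give 49 per arm, which does not match.

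The plan's 60 per arm is therefore correct for the stated score, compared between two arms.

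**2. Ask which score that is.**

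| Place | What is measured | Scale or instrument |
|---|---|---|
| 6.3 | Satisfaction | 0-10, higher is better (Von Frey as alternative) |
| 8.1 main | Satisfaction/comfort with the skin | DLQI |
| 8.1 secondary | Sensitivity; discomfort sensations | Von Frey; brief questionnaire (Annex III per 8.2) |
| 8.2 | Skin satisfaction, and separately satisfaction with the cream | DLQI, and Annex IV |
| Annex IV item 3 | Satisfaction with the cream | 1-10, higher is better |
| 12 | Degree of satisfaction | No instrument named |

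The score in 6.3 resembles Annex IV item 3 apart from the lower end of the scale (0 against 1). No DLQI difference or SD appears anywhere in the documents.

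**3. Does the 95% carry over to the DLQI?** It cannot be shown to. As an illustration only, assume the same 2-point difference on the DLQI and let its SD vary. Power ≈ Φ(2 / (SD × √(2/60)) − 1.96):

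| Assumed SD | Power at 60 per arm |
|---|---|
| 3 | 95% |
| 4 | 78% |
| 5 | 59% |
| 6 | 45% |

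Both the difference and the SDs are assumptions. The table shows only that the power statement belongs to the score it was computed for.

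**4. Who supplies item 3?** Sections 7.2 and 8.2 require Annex IV only from patients who develop discomfort. The form is laid out differently: items 1-3 are put to every user, and a second block is for those with discomfort. If only a fraction of the 60 per arm completed item 3, power for 2 points with SD 3 would be about 72-73% at 50% (30 per arm) and about 90% at 80% (48 per arm). These fractions are assumed. With all 60 it is the planned 95%.

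**5. Does the section 12 test fit item 3?** A paired test of change needs a value before first use. A patient cannot rate satisfaction with a cream not yet applied, so only a comparison of post-treatment values between arms is possible.

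**The case against.** The strongest reply is that the main variable does match a stated aim. The study title, the Summary, the end of section 3, the hypothesis in section 4 and section 6 all speak of skin satisfaction or comfort. PB-011 has one ingredient more than PB-012, so under random allocation a DLQI difference could be a real effect of the cream on the skin. This stands: the DLQI is a defensible main variable, and replacing it would be the sponsor's trade-off.

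It is also fair to say that Annex IV is not missing from the plan. Sections 7.2 and 8.2 collect it; the gap is its absence from 8.1 and from any stated analysis.

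A reader might go further and infer that the DLQI mainly reflects the burden of chemotherapy and neuropathy and so must be the wrong measure. The documents do not support this. Annex II is only referred to as an attachment, so its items cannot be examined.

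A reader might also try to quantify the loss by multiplying the planned difference by an assumed correlation between the DLQI and cream satisfaction. No correlation is given, and the rule fails if the cream acts on skin comfort directly.

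None of this answers the remaining gap: the question in section 4 and the choice in section 2.3 concern the cream, and no variable in 8.1 records the patient's judgement of it.

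**Conclusion.** The point holds as an endpoint-specification gap. The trial sets out to identify the better accepted cream and collects a direct measure of this, but does not list, rank or plan to compare that measure. The sample size is arithmetically sound for a 0-10 satisfaction score (59-60 per arm, about 95% power, two-sided alpha assumed). It gives no assurance for the DLQI, because no DLQI difference or SD is stated.

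The conclusion rests on the protocol's own separation of the two assessments in 7.2 and 8.2, not on any view of the DLQI's content. How much information would be lost by relying on the DLQI cannot be derived from the documents. Nor do they show that the DLQI has to give up its place as main variable.

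**What to change.** 1. **Section 8.1.** List Annex IV item 3 at least as the first-ranked key secondary variable. Add the Annex IV comfort item as a further secondary. Report items 1 and 2 (discomfort and skin reaction, where higher is worse) separately as tolerability, not pooled with item 3.
2. **Section 2.3.** State that the choice of formulation on acceptance rests on item 3.
3. **Section 12.** Specify a two-sample comparison of post-treatment item 3 between PB-011 and PB-012, in place of the paired change test for this item.
4. **Sections 7.2 and 8.2.** State that all cream users complete Annex IV items 1-3, as the form's layout allows, and that the second block remains for those with discomfort.
5. **Sections 6.3, 8.1 and 12.** Name one instrument and scale for each variable, and settle 0-10 against 1-10. If the DLQI stays as main variable, say in 6.3 that the 95% power applies to the satisfaction item and not to the DLQI.

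**Cost.** An amendment to these sections, a short extra questionnaire for patients without discomfort, and one more pre-specified comparison. No new instrument is needed.
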